7. TREATMENT PLAN

7.1. Nintedanib Dosage and Administration

Research participants for this study will initiate treatment with 200mg of oral nintedanib twice per day. The capsules should be swallowed whole (unopened, uncrushed) with a glass of approximately 8 oz. /240 mL of water. Since subjects will be taking oral nintedanib twice daily, the dose interval should be every 12 hours at the same time every day, usually in the morning and the evening after food intake.

In case of a missed dose the subjects should not replace that dose, but proceed to the next scheduled dose when it is due. Each study cycle length is 28 days.

In the event of a treatment delay at the scheduled Day 1 of a cycle, Day 1 of that cycle will be delayed until study treatment is re-started. This may cause a cycle to extend to longer than 28 days. Day 1 will be defined as the day the treatment is re-started.

For dose selection and modifications, see Section 8.

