8. NINTEDANIB INTERRUPTION

8.1. Criteria for Interruption of Treatment with Nintedanib

Treatment with nintedanib will be interrupted according to the criteria listed in Table 1.

In the event of a treatment delay at the time of Day 1 of a cycle, Day 1 of that cycle will be delayed until study treatment is re-started. This may cause a cycle to extend to longer than 28 days.

Table 1: Criteria for interrupting treatment with nintedanib due to an adverse event

If at least one criterion is met, nintedanib will be interrupted:
 
 nausea of CTCAE grade ≥ 3 despite supportive care vomiting of CTCAE grade ≥ 2 despite supportive care diarrhea of CTCAE grade ≥ 2 for more than 3 consecutive days despite supportive care AST and/or ALT elevations of $> 2.5 \times$ ULN in conjunction with bilirubin of $> 1.5 \times$ ULN AST and/or ALT elevations of $> 5 \times$ ULN other non-hematological adverse event of CTCAE grade ≥ 3 considered drug-related Neutropenia grade 3 or 4 and fever $> 38.5^{\circ}\text{C}$ Neutropenia CTCAE grade 4 for more than 7 days without fever Platelets $< 50,000\text{mm}^3$ with bleeding High blood pressure; SBP > 170 mm Hg, or DBP > 100 mm Hg Clinically significant bleeding, CTCAE grade 3 or 4, or grade 2 for 3 or more days
--

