8.2. Criteria to Restart Treatment with Nintedanib

A research participant is eligible to restart nintedanib if all criteria listed in Table 2 are met.

If a subject must interrupt intake of nintedanib due to an adverse event for more than 14 days, the decision to restart treatment with nintedanib needs to be discussed and agreed upon between the sponsor-investigator and the treating physician.

Table 2: Criteria to assess eligibility to restart nintedanib treatment

All criteria must be met in order to restart nintedanib, meaning AEs have to return to Grade 1 or baseline (exception is nausea- see below).
 
  nausea CTCAE grade ≤ 2  vomiting CTCAE grade ≤ 1  diarrhea CTCAE grade ≤ 1  AST and ALT $< 2.5 \times \text{ULN}$; bilirubin $< 1.5 \times \text{ULN}$  no other non-hematological adverse event grade CTCAE ≥ 3 which is considered drug-related  *Neutropenia CTCAE grade ≤ 1, without fever or equal to the subject's pre-therapy value at study enrolment  *Platelets CTCAE grade ≤ 1 or equal to the subject's pre-therapy value at study enrolment  Blood pressure SBP<150 mm Hg; DBP <90 mm Hg  Bleeding CTCAE grade 1 or less
--

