8.3. Dose Adjustments of Nintedanib

As initial measure for the management of side effects (see section 9), treatment with nintedanib should be temporarily interrupted until the specific adverse reaction has resolved to levels that allow continuation of therapy. Nintedanib treatment will be resumed at a reduced dose. Dose adjustments in 100 mg increments per day (i.e. a 50mg reduction per dosing) based on individual safety and tolerability are recommended as described in Table 1. In case of further persistence of the adverse reaction(s), i.e. if a subject does not tolerate 100 mg twice daily, treatment with nintedanib should be discontinued.

The following dose levels will be used in case dose adjustments are required for management of toxicity (see Table 3).

Table 3: Nintedanib dose levels – example for starting dose of 200mg twice daily

Dose-level:	0	-1	-2	-3
Dose:	2 x 200 mg/day	2 x 150 mg/day	2 x 100 mg/day	discontinue treatment

Of note:

If the dose of nintedanib had to be reduced due to toxicity, the subject will stay on the lower dose level for the entire time of administration.

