9. TREATMENT-RELATED ADVERSE EVENTS

9.1. Management of Adverse Events

Based on prior clinical studies with nintedanib, the sponsor investigator should anticipate that any or all of the following AEs could occur. The occurrence of AEs and SAEs should prompt immediate notification to appropriate agencies as outlined in Section 11.6-11.8.

As an initial measure for the management of side effects, treatment with nintedanib should be temporarily interrupted as outlined in Table 1 until the specific adverse reaction has resolved to levels that allow restarting of therapy. Nintedanib treatment may be resumed at a reduced dose as outlined in table 4. Dose adjustments in 100 mg steps per day (i.e. a 50 mg reduction per dosing) based on individual safety and tolerability are recommended as described in Table 4. In case of further persistence of the adverse reaction(s), i.e. if a subject does not tolerate 100 mg twice daily, treatment with nintedanib should be discontinued.

Table 4: Dose adjustments for Nintedanib

CTCAE* Adverse reaction	Dose adjustment
Diarrhea \geq grade 2 for more than 7 consecutive days despite anti- diarrheal treatment** OR diarrhea \geq grade 3 despite anti- diarrheal treatment**	1st episode Reduce dose from 200 mg twice daily to
Vomiting ** \geq grade 2 AND/OR Nausea \geq grade 3 despite anti-emetic treatment**	150 mg twice daily 2nd episode Reduce dose from 150 mg twice daily to
AST and/or ALT elevations of $> 2.5 \times$ ULN in conjunction with bilirubin of $> 1.5 \times$ ULN OR AST and/or ALT elevations of $> 5 \times$ ULN	100 mg twice daily 3rd episode Stop treatment
Other non-haematological or haematological adverse reaction of \geq grade 3	
Elevation of AST and/or ALT values to $> 3 \times$ ULN in conjunction with an increase of total bilirubin to $\geq 2 \times$ ULN and ALKP $< 2 \times$ ULN	Unless there is an alternative cause established, nintedanib should be permanently discontinued

*CTCAE- v4.03: Common Terminology Criteria for Adverse Events

** see also section 9.2.

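### Section 8.3 resumes nintedanib after a hold and cites the wrong table, out of step with the permanent stop in Table 4 and Section 9.2 for one liver pattern

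*Combined protocol and SAP*

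**What the plan says.** **Section 8 (interruption and dose adjustment).** Section 7.1 directs the reader here: "For dose selection and modifications, see Section 8". Table 1 is titled "Criteria for interrupting treatment with nintedanib due to an adverse event". Section 8.2 then says: "A research participant is eligible to restart nintedanib if all criteria listed in Table 2 are met". For interruptions longer than 14 days, Section 8.2 also requires the sponsor-investigator and the treating physician to agree on a restart.

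Section 8.3 begins: "As initial measure for the management of side effects (see section 9), treatment with nintedanib should be temporarily interrupted". The hold lasts until the reaction has recovered enough for therapy to go on. The next sentence is: "Nintedanib treatment will be resumed at a reduced dose". Dose steps of 50 mg per administration "based on individual safety and tolerability are recommended as described in Table 1". The bottom of the ladder is stated as "if a subject does not tolerate 100 mg twice daily, treatment with nintedanib should be discontinued".

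**Section 9 (management of adverse events).** Section 9.1 repeats this paragraph with two differences: "Nintedanib treatment may be resumed at a reduced dose as outlined in table 4", and the steps are again referred to Table 4. The last row of Table 4 covers AST and/or ALT >3x ULN together with total bilirubin ≥2x ULN and ALKP <2x ULN. Its action is a permanent stop unless another cause has been established. Section 9.2 (Hepatic Function) gives the same rule in sequence: interrupt first, then stop for good unless another cause is found.

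**The concern.** Sections 8.3 and 9.1 are meant to be the same instruction, but they differ in the verb and in the table they cite. Section 8.3 states no exception for the permanent-stop liver pattern, and neither does Table 2. Section 7.1 names Section 8 alone for dose modifications, so the less exact text sits where the treatment plan sends the reader.

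At stake is a safety rule. Appendix A describes the potential Hy's Law constellation as very rare but as carrying a poor outlook. A site working from Section 8 alone could re-expose a subject whom Section 9 takes off the drug. Two other places do not help such a reader. Section 3 speaks of withholding treatment until the laboratory values recover, and Appendix A speaks of following subjects until the retreatment criteria are met. Neither repeats the permanent stop.

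**Working it through.** The plan has no figure to reproduce here. The check compares thresholds and then doses.

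**Inputs**
- Hold (Table 1, liver items): AST and/or ALT >2.5x ULN with bilirubin >1.5x ULN, or AST and/or ALT >5x ULN.
- Restart (Table 2, liver item): AST and ALT <2.5x ULN and bilirubin <1.5x ULN.
- Permanent stop (Table 4 last row, Section 9.2): AST/ALT >3x ULN, total bilirubin ≥2x ULN, ALKP <2x ULN, no alternative cause established.
- Dose levels (Table 3): 200, 150 and 100 mg twice daily, then discontinue.

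**Step 1. Does the stop pattern always trigger the hold?** Yes. AST/ALT >3x implies >2.5x, and bilirubin ≥2x implies >1.5x. Every subject with the stop pattern therefore enters the hold that Section 8.3 goes on to describe.

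**Step 2. Can such a subject later satisfy Table 2?** Yes. Take AST 4x, bilirubin 2.5x and ALKP 1x ULN. The hold applies (4 > 2.5 and 2.5 > 1.5), and so does the permanent stop (4 > 3, 2.5 ≥ 2, 1 < 2). After recovery to AST 1x and bilirubin 1x, the Table 2 liver item is met (1 < 2.5 and 1 < 1.5). If the other Table 2 items are also met, the subject is eligible to restart under Section 8.2.

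**Step 3. What dose follows, with no alternative cause established?**

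| Dose before hold | Section 8.3 with Table 3, read literally | Table 4 last row and Section 9.2 |
|---|---|---|
| 200 mg twice daily (400 mg/day) | 150 mg twice daily (2 × 150 = 300 mg/day) | 0 |
| 150 mg twice daily (300 mg/day) | 100 mg twice daily (2 × 100 = 200 mg/day) | 0 |
| 100 mg twice daily (200 mg/day) | discontinue (0) | 0 |

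The two readings differ at two of the three dose levels. They agree at 100 mg twice daily. If an alternative cause is established, the permanent stop does not apply and there is no difference.

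**Step 4. Is the table citation right?** No. Table 1 has 11 interruption criteria and 0 dose adjustments. Table 3, within Section 8.3, gives the dose levels. The adjustments by adverse reaction and episode are in Table 4, which Section 9.1 cites.

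**The case against.** The strongest reply is that Section 8.3 should be read as a whole. Its first sentence refers to Section 9, and resumption follows only once the reaction has recovered enough for therapy to continue. Section 9 says this liver pattern does not permit continuation unless another cause is established. The sentence on resuming can also be read as fixing the dose at restart (reduced, not full) rather than ordering a restart in every case. Table 4 itself relies on a specific row overriding a general one: the stop pattern also meets its reduce-the-dose liver row, and nobody would take that as permission to continue. The specific rule appears twice, and a careful reader would probably apply it.

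Most of this stands. A reader might infer that the two sections flatly contradict each other, so that no site could comply with both, or that Section 8.2 orders a restart. The documents do not support either. The reference to Section 9 and the recovery condition leave room for a consistent reading, and Section 8.2 sets eligibility only. For holds over 14 days it also requires the sponsor-investigator's agreement.

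The reply does not remove the ambiguity. The recovery condition can equally be read as meaning the Table 2 values, which contain no exception. The agreement requirement does not reach holds of 14 days or less. The citation of Table 1 is wrong on any reading.

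**Conclusion.** Section 8.3 is inconsistent with Section 9 in its verb and its table citation, and it omits an exception that Section 9 states. Read literally with Table 2, it would restart a recovered subject at 300 or 200 mg/day where Table 4 and Section 9.2 require a permanent stop. This rests on three conditions: the subject was on 200 or 150 mg twice daily, met the full liver pattern with no established alternative cause, and later met all Table 2 criteria.

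Practical risk is low. Appendix A calls potential Hy's Law cases very rare. Liver events of this kind are reported to the sponsor-investigator within 24 hours (Section 11.4.1), and Appendix A recommends repeat tests and evaluation within 48 hours. Section 7.3 allows a stop for an unacceptable adverse event or on the investigator's judgement. The documents give no rate for the pattern, so no number of affected subjects is claimed.

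A reader might also infer that the trial's results are affected. They are not: no endpoint definition, sample size, error rate or other statistical figure depends on this text. It is an internal inconsistency in a safety rule, of minor severity, and not a questionable design choice.

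**What to change.** In Section 8.3, change *will* to *may* in the sentence on resuming, change the citation from Table 1 to Table 4, and add: *except where Table 4 or Section 9.2 requires permanent discontinuation*. Add the same exception to Section 8.2 and Table 2, so that meeting the recovery values does not by itself make such a subject eligible to restart. Optionally, have Section 7.1 point to Sections 8 and 9; the existing reference to Section 9 within Section 8.3 makes this less pressing.

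The cost is a few words of text. No visit, test or subject is added, and no analysis changes.

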9. TREATMENT-RELATED ADVERSE EVENTS

9.1. Management of Adverse Events

Based on prior clinical studies with nintedanib, the sponsor investigator should anticipate that any or all of the following AEs could occur. The occurrence of AEs and SAEs should prompt immediate notification to appropriate agencies as outlined in Section 11.6-11.8.

As an initial measure for the management of side effects, treatment with nintedanib should be temporarily interrupted as outlined in Table 1 until the specific adverse reaction has resolved to levels that allow restarting of therapy. Nintedanib treatment may be resumed at a reduced dose as outlined in table 4. Dose adjustments in 100 mg steps per day (i.e. a 50 mg reduction per dosing) based on individual safety and tolerability are recommended as described in Table 4. In case of further persistence of the adverse reaction(s), i.e. if a subject does not tolerate 100 mg twice daily, treatment with nintedanib should be discontinued.

Table 4: Dose adjustments for Nintedanib

CTCAE* Adverse reaction	Dose adjustment
Diarrhea \geq grade 2 for more than 7 consecutive days despite anti- diarrheal treatment** OR diarrhea \geq grade 3 despite anti- diarrheal treatment**	1st episode Reduce dose from 200 mg twice daily to
Vomiting ** \geq grade 2 AND/OR Nausea \geq grade 3 despite anti-emetic treatment**	150 mg twice daily 2nd episode Reduce dose from 150 mg twice daily to
AST and/or ALT elevations of $> 2.5 \times$ ULN in conjunction with bilirubin of $> 1.5 \times$ ULN OR AST and/or ALT elevations of $> 5 \times$ ULN	100 mg twice daily 3rd episode Stop treatment
Other non-haematological or haematological adverse reaction of \geq grade 3	
Elevation of AST and/or ALT values to $> 3 \times$ ULN in conjunction with an increase of total bilirubin to $\geq 2 \times$ ULN and ALKP $< 2 \times$ ULN	Unless there is an alternative cause established, nintedanib should be permanently discontinued

*CTCAE- v4.03: Common Terminology Criteria for Adverse Events

** see also section 9.2.

9.2. Additional Precautions for Nintedanib

- *Diarrhea*
Diarrhea was the most frequently reported gastro-intestinal event and appeared in close temporal relationship with the administration of docetaxel in

the clinical trial LUME-Lung 1¹⁰. The majority of subjects had mild to moderate diarrhea. 6.3 % had diarrhea of grade ≥ 3 in combination treatment compared to 3.6 % treated with docetaxel alone. Diarrhea should be treated at first signs with adequate hydration and anti-diarrheal medicinal products, e.g. loperamide, and may require interruption, dose reduction or discontinuation of therapy with nintedanib.

- *Nausea and vomiting*

Nausea and vomiting, mostly of mild to moderate severity, were frequently reported gastrointestinal adverse events in the clinical trial LUME-Lung 1¹⁰. Interruption, dose reduction or discontinuation of therapy with nintedanib may be required despite appropriate supportive care. Supportive care for nausea and vomiting may include medicinal products with anti-emetic properties, e.g. glucocorticoids, anti-histamines or 5-HT₃ receptor antagonists and adequate hydration.

In the event of dehydration, administration of electrolytes and fluids is required. Plasma levels of electrolytes should be monitored, if relevant gastrointestinal adverse events occur.

- *Neutropenia and Sepsis*

A higher frequency of neutropenia of CTCAE grade ≥ 3 was observed in subjects treated with nintedanib in combination with docetaxel as compared to treatment with docetaxel alone in the clinical trial LUME-Lung 1¹⁰. Subsequent complications such as sepsis or febrile neutropenia have been observed.

Blood counts should be monitored during therapy, if nintedanib (BIBF 1120) is combined with a myelosuppressive agent.

- *Hepatic Function*

The safety and efficacy of nintedanib has not been studied in patients with moderate (Child Pugh B) or severe (Child Pugh C) hepatic impairment. Therefore, treatment with nintedanib is not recommended in such patients.

Administration of nintedanib was associated with an elevation of liver enzymes (ALT, AST, ALKP (alkaline phosphatase), and bilirubin), with a potentially higher risk for female patients.

These increases were reversible in the majority of cases and not associated with clinically manifest liver disorders. Hepatic transaminases, ALKP and

bilirubin levels are recommended to be closely monitored after start of therapy with nintedanib.

If relevant liver enzyme elevations are measured, interruption, dose reduction or discontinuation of the therapy with nintedanib may be required (Refer to Table 4).

Alternative causes of the liver enzyme elevations should be investigated and respective action should be taken as necessary. In case of specific changes in liver values (AST/ALT > 3 x ULN; total bilirubin \geq 2 x ULN and ALKP < 2 x ULN) treatment with nintedanib should be interrupted. Unless there is an alternative cause established, nintedanib should be permanently discontinued.

- *Special populations*

Nintedanib exposure increased linearly with patient age, was inversely correlated to weight, and was generally higher in patients of Asian race. This may result in a higher risk of developing liver enzyme elevations. Close monitoring is recommended in patients with several of these risk factors. In study 1199.13 (LUME-Lung 1), there was a higher frequency of SAEs in patients treated with nintedanib plus docetaxel with a body weight of less than 50 kg compared to patients with a weight \geq 50 kg; however, the number of patients with a body weight of less than 50 kg was small. Therefore, close monitoring is recommended in patients weighing < 50 kg.

9.3. Rescue Medications and Additional Treatments

Rescue medication to reverse the actions of nintedanib is not available. Potential side effects of nintedanib should be treated symptomatically.

9.4. Restrictions

The following are not permitted during study treatment:

- Other anti-neoplastic investigational treatment for appendiceal cancer .
- Systemic antitumor therapy, including cytotoxic therapy, signal transduction inhibitors, immunotherapy, radiotherapy and hormonal therapy .
- Bone marrow transplant or stem cell rescue.
- Therapeutic anticoagulation with drugs requiring INR monitoring (except low-dose heparin and/or heparin flush as needed for maintenance of an in-dwelling intravenous device) or anti-platelet therapy (except for low-dose therapy with acetylsalicylic acid \leq 325mg per day).

The following are permitted during study treatment and will require additional/close monitoring:

- Strong P-gp inhibitors may increase exposure to nintedanib (e.g. ketoconazole or erythromycin). In such cases patients should be monitored closely for tolerability of nintedanib. Management of side effects may require interruption, dose reduction or discontinuation of therapy with nintedanib.
- Strong CYP3A4 and P-gp inducers, including but not limited to rifampicin, carbamazepine, phenytoin, and St. John's Wort (please see Appendix B), may decrease exposure to nintedanib. Co-administration with nintedanib should be carefully considered and closely monitored. Use of herbal remedies is discouraged, and is permitted only with the specific assent of the Investigator. All herbal and vitamin supplement use must be carefully documented.
- Subjects taking narrow therapeutic index medications should be monitored proactively (e.g. phenytoin, quinidine, carbamazepine, phenobarbital, cyclosporine, and digoxin).

10. DATA AND SAFETY MONITORING PLAN

10.1. Safety Monitoring

This protocol will be monitored according to the processes in effect for all Levine Cancer Institute investigator- initiated studies and the protocol-specific monitoring plan, and will abide by standard operating procedures set forth by both the Carolinas HealthCare System Office of Clinical and Translational Research and the Levine Cancer Institute Clinical Trials Office. It is the responsibility of the Sponsor-Investigator to monitor the safety data for this study. The Sponsor-Investigator, Statistician, and other team members as needed will meet regularly to monitor subject consents, enrollment and retention, safety data for all subjects [including adverse events (AE's) for all grades and attributions, serious adverse events (SAE's)], study drug administration, and validity/integrity of the data. Documentation of these meetings will be kept with study records. SAEs will be reported to the IRB per their requirements. Major protocol deviations that in the Investigator's judgment potentially caused harm to participants or others or indicate that the participants or others are at an increased risk of harm, or has adversely impacted data integrity will be reported to the IRB per their requirements. The Sponsor-Investigator will submit data to the LCI Data and Safety Monitoring Committee according to the overarching LCI Data and Safety Monitoring Plan.

10.2. Data Quality Assurance

This study will be organized, performed, and reported in compliance with the study protocol, standard operating procedures (SOPs) of the Levine Cancer Institute and Carolinas HealthCare System Office of Clinical and Translational Research, and other applicable regulations and guidelines (e.g. GCP).

Data will be collected on electronic Case Report Forms (eCRFs).

Subjects will be monitored by Levine Cancer Institute Research Monitors routinely for data quality. This monitoring will be done by comparing source documentation to the eCRFs. The study database will be reviewed and checked for omissions, apparent errors, and values requiring further clarification using computerized and manual procedures. Data queries requiring clarification will be generated and addressed by the appropriate research personnel. Only authorized personnel will make corrections to the study database and all corrections will be documented in an electronic audit trail.

